[figure not shown]
[figure not shown]
[figure not shown]

Clinical Trial Protocol

Document Number:		c26581385-02
EudraCT No. EU Trial No.	N/A	
BI Trial No.	1368-0037	
BI Investigational Medicinal Product(s)	BI 655130	
Title	An open label extension study to assess the long term safety of treatment with BI 655130 administered subcutaneously in adult patients with moderate to severe atopic dermatitis.	
Lay Title	A study to test the long-term safety of BI 655130 in patients with atopic eczema who took part in study 1368-0032	
Clinical Phase	II	
Clinical Trial Leader	 Tel:  Fax: 	
Coordinating Investigator	N/A	
Status	Final Protocol (Revised Protocol based on Global Amendment 1)	
Version and Date	Version: 2.0	Date: 23 March 2020
Page 1 of 73		
Proprietary confidential information. © 2020 Boehringer Ingelheim International GmbH or one or more of its affiliated companies. All rights reserved. This document may not - in full or in part - be passed on, reproduced, published or otherwise used without prior written permission.		

CLINICAL TRIAL PROTOCOL SYNOPSIS

Company name	Boehringer Ingelheim
Protocol date	07 May 2019
Revision date	23 Mar 2020
BI trial number	1368-0037
Title of trial	An open label extension study to assess the long term safety of treatment with BI 655130 administered subcutaneously in adult patients with moderate to severe atopic dermatitis.
Coordinating Investigator	N/A
Trial site(s)	Multi-centre trial
Clinical phase	II
Trial rationale	To provide patients with moderate to severe atopic dermatitis extended access to a potentially beneficial treatment and evaluate long-term tolerability and safety
Trial objective(s)	The primary objective of this trial is to assess the long term safety and efficacy of treatment with BI 655130 in patients with atopic dermatitis who have completed and have responded to treatment in the parent study 1368-0032.
Trial endpoints	
Primary Endpoint
 
 Number of patients with treatment emergent adverse events (AEs) at week 48 
Secondary endpoints
 
 Percentage change from baseline in the Eczema Area and Severity Index (EASI) Score at Week 48 Percentage of patients with a 50% improvement from baseline in EASI (EASI50) at Week 48 Percentage of patients with a 75% improvement from baseline in EASI (EASI75) at Week 48 Change from baseline in SCORing of Atopic Dermatitis (SCORAD) (%) at Week 48 Percentage of patients achieving at least a 2-grade reduction from baseline to clear (0) or almost clear (1) in Investigator Global Assessment (IGA) at Week 48
Trial design	An open label extension clinical trial consisting of approximately 4 years of treatment and a 16 week follow-up
Total number of patients randomised	Approximately 40 patients will enter this trial
Number of patients on each treatment	All patients will receive BI 655130
Diagnosis	Adult patients with moderate to severe atopic dermatitis
Main in- and exclusion	Inclusion Criteria


criteria
	
• Signed and dated written informed consent in accordance with Good Clinical Practice (GCP) and local legislation prior to the start of any screening procedures• Patients who completed the 1368-0032 trial and did not prematurely discontinue treatment prior to week 16, and; In the 1368-0032 re-allocation period (V7 to V11) :
➢ If an original non-responder from week 16 (V7), attained at least an EASI 50 by last infusion (week 28) or by the EOS.➢ If an original responder from week 16 (V7) completed the last visit Week 28 (EOS) or dropped to an EASI 50 score prior to Week 28. 
Women of childbearing potential (WOCBP)¹ must be ready and able to use highly effective methods of birth control per ICH M3 (R2) that result in a low failure rate of less than 1% per year when used consistently and correctly for the duration of the trial and 16 weeks after last administration. A list of contraception methods meeting these criteria is provided in the patient information. (Refer to Section 4.2.2.3)
 
¹A woman is considered of childbearing potential (WOCBP), i.e. fertile, following menarche and until becoming post-menopausal unless permanently sterile. Permanent sterilisation methods include hysterectomy, bilateral salpingectomy and bilateral oophorectomy. Tubal ligation is NOT a method of permanent sterilisation. A postmenopausal state is defined as no menses for 12 months without an alternative medical cause.
 
Exclusion Criteria
 
• Women who are pregnant, nursing, or who plan to become pregnant while in the trial. (Refer to Section 4.2.2.3)• Any new documented active or suspected malignancy except appropriately treated basal cell carcinoma, squamous cell carcinoma of the skin or in situ carcinoma of uterine cervix.• Use of any restricted medication as specified in Section 4.2.2.1 or any drug considered likely to interfere with the safe conduct of the study, as assessed by the investigator.• Active systemic infections during the last two weeks prior to first drug administration.• Currently enrolled in another investigational device or drug trial, except for 1368-0032.• Any condition which would prevent the patient continuing on treatment in this trial 1368-0037
-----------------	---

	
History of allergy/hypersensitivity to the systemically administered trial medication agent or its excipients
Test product(s)	BI 655130
dose	600 mg (4 syringes, 150 mg each) every 4 weeks
mode of administration	Subcutaneous (SC)
Comparator product(s)	N/A
dose	N/A
mode of administration	N/A
Duration of treatment	Approximately 4 years
Statistical methods	Descriptive statistics only

FLOW CHART- YEAR 1

	Open Label Treatment Period- Year 1													
Visit Number	1 ²	2	3	4	5	6	7	8	9	10	11	12	13	14
Day	1	29	57	85	113	141	169	197	225	253	281	309	337	365
Week	1	4	8	12	16	20	24	28	32	36	40	44	48	52
Visit Window (days)	n/a	±14	±14	±14	±14	±14	±14	±14	±14	±14	±14	±14	±14	±14
Visit Type	A	B	B	C	B	B	D	B	B	C	B	B	E	B
Informed consent ¹	X													
Demographics	X													
Medical history	X													
Inclusion/Exclusion/Eligibility	X													
Smoking status/weight/height ¹⁸	X												X	
Physical exam	X ⁸	X ⁹	X ⁹	X ⁹	X ⁹	X ⁹	X ⁹	X ⁹	X ⁹	X ⁹	X ⁹	X ⁹	X ⁸	X ⁹
Vital signs ¹⁰	X	X	X	X	X	X	X	X	X	X	X	X	X	X
12 lead-ECG ⁵	X												X	
Safety Lab tests ¹¹	X						X						X	
Pregnancy Testing ⁷	X	X	X	X	X	X	X	X	X	X	X	X	X	X
Infection Testing ¹²	X												X	
VAS SCORAD ⁶	X			X			X			X			X	
														
IGA ⁶ EASI ⁶ SCORAD ⁶	X			X			X			X			X	
														
														
														
All AEs/SAEs/AESIs ³	X	X	X	X	X	X	X	X	X	X	X	X	X	X
Concomitant therapy	X	X	X	X	X	X	X	X	X	X	X	X	X	X
IRT Call	X ¹⁶	X	X	X	X	X	X	X	X	X	X	X	X	X
Administer trial drugs	X	X	X	X	X	X	X	X	X	X	X	X	X	X

Continue year 2 to 4 based on visit type (See Flow Chart for Years 2-4 and Flow Chart for end of treatment and end of study visits.)

FLOW CHART- YEARS 2-4

The same visit schedule repeats yearly until the end of year four as follows.
 These treatment visits will follow the same ±14 day visit window

Year 2													
Visit	15	16	17	18	19	20	21	22	23	24	25	26	27
Day	393	421	449	477	505	533	561	589	617	645	673	701	729
Week	56	60	64	68	72	76	80	84	88	92	96	100	104
Visit Type	B	B	C	B	B	D	B	B	C	B	B	E	B
Year 3*													
Visit	28	29	30	31	32	33	34	35	36	37	38	39	40
Day	757	785	813	841	869	897	925	953	981	1009	1037	1065	1093
Week	108	112	116	120	124	128	132	136	140	144	148	152	156
Visit Type	B	B	C	B	B	D	B	B	C	B	B	E	B
Year 4*													
Visit	41	42	43	44	45	46	47	48	49	50	51	EOT (52)	EOS (53)
Day	1121	1149	1177	1205	1233	1261	1289	1317	1345	1373	1401	1429	1541
Week	160	164	168	172	176	180	184	188	192	196	200	204	220
Visit Type	B	B	C	B	B	D	B	B	C	B	B	EOT	EOS

Footnotes to Flow Chart:

[figure not shown]
1. Patients should sign consent on or prior to visit 1 (V1).
2. V1 of this extension trial should be preferably performed during the EOS of the preceding BI 655130 parent trial. When the visits are performed on the same day duplicate procedures across studies are performed once during the EOS/V1. If these visits are not performed on the same day then all V1 procedures need to be performed at that visit. The only exception is Infection Testing which does not have to be repeated if performed at EOS of the parent trial and there is a <12 week gap from EOS of parent trial to V1 of this trial. Refer also to [Section 6.2.1](#)
3. After the individual patient's end of the trial the investigator should report only any cancers of new histology and exacerbations of existing cancer, study treatment related SAEs and study treatment related AESIs of which the investigator may become aware of and only via the BI SAE form. Refer to [Section 5.2.6.2.1](#).
4. All patients who receive at least one dose in the trial, including those who discontinue treatment prematurely, should complete the EOT visit as soon as possible and complete the EOS visit 16 weeks after the date of last trial drug administration.
5. Where possible, electrocardiogram (ECG) measurements should precede blood sampling and drug administration. Refer to [Section 5.2.4](#)
6. Body Surface Area (BSA) will be calculated from Part A of the SCORAD. All assessments must be done prior to trial drug administration. The questionnaires completed by patients should be done first before the investigator assessments. Refer to [Section 6.2](#)
7. Only applicable for women of childbearing potential. Urine pregnancy tests will be performed at all visits indicated in the [Flow Chart](#). Urine pregnancy testing should be done prior to administration of study drug. Study drug should only be administered in case of a negative test result. In case of a positive urine pregnancy test, a serum pregnancy test will be performed at the central laboratory.
8. Complete Physical Examination (PE) includes general appearance as well as evaluation of all organ systems.
9. Targeted physical examination includes evaluation of organ systems associated with AE(s) symptoms or laboratory abnormalities.
10. Vital signs will be assessed pre dose as well as within 1 hour post dose.
11. Safety laboratory tests include clinical chemistry, haematology, coagulation, and urinalysis, and will be performed centrally. Where possible, safety laboratory tests are to be drawn prior to dosing.
12. Infection testing includes tuberculosis, hepatitis B, hepatitis C, and HIV assessments. Refer to [Table 5.2.3:1](#) and [Section 6.2.1](#). During a combined EOS/V1 only hepatitis C and HIV assessments will need to be done while results of tuberculosis and hepatitis B will be used from the parent trial.
13. At EOT visit, infection testing and ECG are only required if not done within the past 6 months.
14. 
15. For patients who complete the trial, the EOT visit will be the last treatment administration. For patients who discontinue early, there will be no treatment administration at the EOT visit.
16. There will be two IRT calls needed at Visit 1. The first is the study enrolment call performed after the patient signs consent; the second call is a "medication assignment" call performed after confirming eligibility to dispense the first dose of medication.
17. If a patient completes the trial and week 204 (Visit 52) is the EOT, then the site will need to make 2 IRT transactions- one transaction to dispense last medication, and another transaction to complete treatment. For patients who discontinue early, there will be 1 IRT call (transaction) to discontinue treatment.
18. Height is collected at Visit 1 only.

TABLE OF CONTENTS

TITLE PAGE	1
CLINICAL TRIAL PROTOCOL SYNOPSIS	2
FLOW CHART- YEAR 1	5
FLOW CHART- YEARS 2-4.....	6
FLOW CHART: END OF TREATMENT AND END OF STUDY VISITS	7
TABLE OF CONTENTS	9
ABBREVIATIONS	13
1. INTRODUCTION.....	16
1.1 MEDICAL BACKGROUND	16
1.2 DRUG PROFILE	17
1.2.1 Mode of Action	17
1.2.1.1 Residual Effect Period	17
1.2.1.2 Key pharmacokinetic characteristics	17
1.2.3 Clinical Experience	18
1.3 RATIONALE FOR PERFORMING THE TRIAL	19
1.4 BENEFIT - RISK ASSESSMENT.....	20
1.4.1 Benefits.....	20
1.4.2 Risks	20
1.4.3 Discussion.....	23
2. TRIAL OBJECTIVES AND ENDPOINTS.....	24
2.1 MAIN OBJECTIVES, PRIMARY AND SECONDARY ENDPOINTS.....	24
2.1.1 Main objectives.....	24
2.1.2 Primary endpoint	24
2.1.3 Secondary endpoints.....	24
3. DESCRIPTION OF DESIGN AND TRIAL POPULATION	26
3.1 OVERALL TRIAL DESIGN AND PLAN	26
3.2 DISCUSSION OF TRIAL DESIGN, INCLUDING THE CHOICE OF CONTROL GROUP(S)	27
3.3 SELECTION OF TRIAL POPULATION	27
3.3.1 Main diagnosis for trial entry	27
3.3.2 Inclusion criteria	28
3.3.3 Exclusion Criteria	29
3.3.4 Withdrawal of patients from treatment or assessments.....	29
3.3.4.1 Discontinuation of trial treatment	30
3.3.4.2 Withdrawal of consent to trial participation	31

3.3.4.3	Discontinuation of the trial by the sponsor	31

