1. INTRODUCTION

1.1 MEDICAL BACKGROUND

Atopic Dermatitis (AD) is an immune-mediated skin disease characterized by chronic or relapsing red and inflamed skin (erythema) and an intense and unrelenting itch (pruritus). In common terminology AD is often referred to as Eczema, the term for a variety of skin conditions, of which AD is the most severe. Diagnosis is based on a patient's medical history, characteristic clinical findings and exclusion of other skin conditions [P18-07868]. The hallmark of AD is pruritus that is responsible for much of the disease burden for patients and their families. Pruritus can be persistent and consequently can disrupt sleep and/or cause anxiety or depression [R18-2681, R18-2680]. Other clinical features of AD include skin dryness, erythema (redness), oozing, crusting, and lichenification (skin that has become thickened and leathery).

Worldwide, the lifetime prevalence of AD has increased over the last 30 years occurring in 10–20% of the population in developed countries. Prevalence is lower, but increasing, in developing countries [R18-2667]. Typically, AD develops during childhood with approximately 60% of cases occurring in the first year of life [P06-08156; R18-2668]. In about 70% of cases, the disease greatly improves or resolves in childhood, but the remaining 30% of patients go on to have a remitting and relapsing condition with repeated flares [R18-2668; R18-2663].

AD appears to have a more heterogeneous pathophysiology than previously thought. Unlike chronic plaque psoriasis that is almost exclusively driven by the Th17 pathway, AD involves multiple immune axes involving expression of multiple cytokines and chemokines, including Interleukin (IL)-13, IL-4, IL-33, and IL-22.

In human skin tissues, IL36R is expressed in keratinocytes, dermal fibroblasts and infiltrating myeloid cells. IL36R activation in skin tissue drives the production of inflammatory mediators (e.g. CCL20, MIP-1 β , TNF- β , IL12, IL17, IL23, TGF- β) and modulates the expression of tissue remodeling genes (e.g. MMPs, TGF- β). The link between IL36R and AD is based on data demonstrating upregulation of human IL36R and IL36 (and IL36 α) expression in AD skin biopsies compared to normal control skin as well as data showing IL36R functionality in disease relevant primary human cells. In addition, there is data demonstrating enhanced IL-36 signaling in human macrophages via the TH2 cytokine (IL4) pathway.

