3.3.1 Main diagnosis for trial entry

Patients with AD will be included in this trial if they fulfil all the inclusion and do not present any of the exclusion criteria.

Patients who prematurely discontinued blinded treatment (up to Week 16) in the parent trial (1368-0032) are not eligible for this study. In addition patients from 1368-0032 must have

shown a response in order to be eligible. Patients from the 1368-0032 who were in the non-responder category at week 16, which was defined as less than EASI 75, must have completed the EOS visit and must attain at least an EASI 50 by the last infusion of BI 655130 (Week 28) or by the EOS in order to be eligible for this extension trial.

Patients from the 1368-0032 who were in the responder category at week 16 (V7) which was defined as an EASI 75 or greater, are eligible as long as they have completed the (EOS) visit. If this patient drops to an EASI 50 score prior to the planned EOS at Week 28, they will immediately perform EOS in 1368-0032 and enter into this extension trial.

Patients should enrol into the extension trial as soon as possible after conclusion of the parent trial. It is preferred that the end of study (EOS) visit from parent trial (1368-0032) will be combined with Visit 1 of this trial which includes the first SC dose of trial drug. The Sponsor must be notified if enrolment is delayed. Patients must be enrolled within a maximum of 12 weeks after the EOS visit from 1368-0032. (Refer to [Section 6.2.1](#) for more detailed information on study procedures).

The results of the safety labs as well as Infection Testing will be available/reported after the patient has entered and received the first dose of study medication in this trial. Refer to [Section 3.3.4.1](#) for discontinuation of treatment rules.

Please refer to [Section 8.3.1](#) (Source Documents) for the documentation requirements pertaining to the in- and exclusion criteria.

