- **"Speso 600 mg SC q4w" followed by "no Speso 600 mg SC q4w"** – patients who were randomised to receive active treatment (Speso) in the double-blind period of the parent trial and didn't receive Speso treatment in the open-label period of the parent trial (but didn't discontinue the parent study prematurely)
- **"Overall Total"** – all patients from FAS, regardless of the treatment received in the parent trial.

2. By the response achieved at Week 16 of the parent trial (1368-0032):

- **"Responders"** – patients who attained at least 75% reduction in EASI score at Week 16 compared to baseline during the parent trial
- **"Non-responders"** – patients who attained less than 75% reduction in EASI score at Week 16 compared to baseline during the parent trial
- **"Overall Total"** – all patients from FAS, regardless of the EASI response status at Week 16 in the parent trial.

More details on the technical implementation of these analyses are provided in the ADS Plan of this TSAP.

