6.7 BASELINE, TIME WINDOWS AND CALCULATED VISITS

Measurements reported with date and time and taken prior to start of administration of trial treatment will be considered pre-treatment values. Measurements reported with a date only (and no time) and taken on the day of first administration of trial treatment will also be considered pre-treatment values. These pre-treatment values will be assigned to visits according to the nominal visit number as recorded on the eCRF or as provided by the laboratory. For definitions used in Safety analyses, refer to [Section 7.8](#).

There will be two different baseline definitions used in the analyses:

1. Baseline for this extension trial – defined as the last measurement recorded before the first trial medication administration in this study.

2. Baseline for the parent trial (1638-0032) – defined as the measurement recorded at randomisation visit (Visit 2) of the parent trial. If the data at Visit 2 is missing, then the data from Visit 1 of the parent trial will be considered baseline.

Two separate analyses will be conducted, using the baselines as defined above.

Measurements taken after start of administration of trial treatment will be considered either on- or off-treatment values based on the definition in [Section 6.1](#), and will be assigned to visits for statistical analysis, if applicable, as defined below.

Analysis of AE data, concomitant medication or non-drug therapies will not be based on visits. Therefore, no assignment to time windows will be necessary for such data.

For derivation of the last value on treatment, minimum value on treatment, and maximum value in the trial phase, all values from the relevant phase (whether or not collected in any time window; see [Table 6.1: 1](#) for definition of the trial phases) will be considered; these will be derived for analysis of laboratory and vital signs data. For identification of potentially clinically significant abnormal laboratory values, all values (whether or not selected in any time window) before the date of EoS Participation visit will be considered.

A graphical analysis of the ALT and total bilirubin will be performed (so called eDISH plot) based on the available data obtained during the on-treatment period.

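### Week-16 responders who enter on losing response can have the triggering EASI as their extension baseline, and SAP 6.1 pools them with responders who completed Week 28

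*Protocol*

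**What the plan says.** - **Two entry routes.** Under the Protocol synopsis and section 3.3.2, a Week-16 responder qualifies having "completed the last visit Week 28 (EOS) or dropped to an EASI 50 score prior to Week 28". For the second route, Protocol 3.3.1 says that "they will immediately perform EOS in 1368-0032 and enter into this extension trial".
- **Combined visit.** Flow Chart footnote 2 says "V1 of this extension trial should be preferably performed during the EOS of the preceding BI 655130 parent trial". It continues: "When the visits are performed on the same day duplicate procedures across studies are performed once during the EOS/V1". Otherwise, "If these visits are not performed on the same day then all V1 procedures need to be performed at that visit". Protocol 6.2.1 allows a gap of up to 12 weeks.
- **Extension baseline.** SAP 6.7 has it "defined as the last measurement recorded before the first trial medication administration in this study"; Protocol 7.2.1 agrees. It is a single value, with no averaging.
- **Second baseline.** Both documents also plan a separate analysis from the parent-trial randomisation baseline.
- **Groups.** SAP 6.1 defines Responders only as "patients who attained at least 75% reduction in EASI score at Week 16 compared to baseline during the parent trial". The other grouping is by parent treatment sequence. In the visible text neither separates the two entry routes.
- **Disease course.** Protocol 1.1 says that the patients whose disease does not improve or resolve in childhood go on to have "a remitting and relapsing condition with repeated flares".

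**The concern.** A score that is selected because it was bad will, on average, be better at a later visit even if nothing is done. If that score is also the baseline, the recovery appears as improvement on treatment.

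There is a second problem that does not depend on noise. A patient who has lost half of the parent-trial improvement has room to improve again; a patient still at EASI 75 has much less. One Responders column then answers two questions at once: was a response held, and was a lost response regained?

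The tables affected are the extension-baseline displays of EASI change, EASI50 and EASI75, and probably the correlated SCORAD and IGA results, in the Responders and Overall Total columns. Efficacy is part of the stated primary objective (Protocol 2.1.1), and status reviews may feed submissions and publications (Protocol 7.2.7).

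**Working it through.** The plan gives no figure to reproduce: the sample of about 40 is not calculated and all analyses are descriptive.

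**Step 1. Pooling, by arithmetic alone.** SAP 5.2.2 counts a patient as EASIxx if 100 × (baseline − current) / baseline ≥ xx. Let P be the parent baseline EASI.

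- Enters at exactly EASI 50 (0.50P) and returns to exactly EASI 75 (0.25P): 100 × (0.50P − 0.25P) / 0.50P = 50%, an EASI50 responder on the extension baseline. With P = 25 the score goes from 12.5 to 6.25.
- Holds EASI 75 throughout (0.25P to 0.25P): 0%, an EASI50 non-responder on the extension baseline.

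For the same P both finish at the same EASI, and both are EASI75 responders on the parent baseline.

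**Step 2. Regression to the mean, with no drug effect.** None of these inputs is in the documents:

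- ln(EASI) = ln(25 × (1 − 0.75)) + patient effect + visit error
- patient effect SD 0.5; visit error SD 0.3 to 0.7, with 4-week autocorrelation 0.3 to 0.6
- keep patients with Week-16 EASI ≤ 0.25 × 25 = 6.25
- relapse entry at the first of Weeks 20 and 24 with EASI ≥ 0.50 × 25 = 12.5, and that score is the baseline; all others take Week 28 as baseline
- extension Week-48 score drawn from the same patient level

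| Quantity (trigger: improvement of 50% or less) | Range over scenarios |
|---|---|
| Relapse entrants, share of responders | about 0.3% to 17% |
| Relapse entrants, median change | about -41% to -60% |
| Relapse entrants reaching EASI50 | about 32% to 61% |
| Week-28 completers, median change | about 0% to +17% |
| Pooled Responders, median change | about +6% to -12% |
| Shift in pooled median from including relapse entrants | under 1 to about 17 points |
| Shift in pooled EASI50 | about 0.1 to 7 percentage points |

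The two ends of these ranges belong to different scenarios. The -41% arises where about 1% or fewer of responders relapse: 0.01 × 40 = 0.4 of a patient, even if all 40 were Week-16 responders. The 17-point shift arises at visit-error SD 0.7: pooled about -12% against about +5% without relapse entrants. Part of that gap is mirror-image selection, because completers are those who did not score badly at Week 20 or 24.

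**Step 3. Changing the assumptions.**

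- Trigger read as any fall below EASI 75: relapse-subset median about -17% to -40%, with more relapsers.
- Lasting loss of effect of 0.3 log units per visit: about -22% to -48%, again with more relapsers.
- Different model, with additive noise in percentage points of improvement, true loss of 0 to 15 points per visit and no treatment effect:

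| Noise SD | Fall in mean EASI, relapse entrants | Their EASI50 | Fall, pooled responders |
|---|---|---|---|
| 5 | 6% to 20% | up to 0.4% | 0% to 2% |
| 10 | 15% to 38% | 5% to 29% | 1.5% to 7% |
| 15 | 22% to 46% | 16% to 45% | 10% to 12% |

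(At SD 5 with no true loss, nobody relapsed.) The direction is the same throughout; the size is not settled. The 17-point and 7-percentage-point figures belong to the Step 2 model and are not upper limits where relapse is more common.

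**The case against.** **A parent-baseline analysis is already planned.** This stands, and it matters: that analysis does not use the entry-day score. But neither analysis is named as leading, and an unaffected second table does not correct the first.

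**Same-day entry is only preferred.** This also stands. If Visit 1 is later, EASI is scored again and the artefact shrinks. In the Step 2 model the part carried by a single score falls with the autocorrelation. A four-week delay still leaves a median of about -16% to -40%; at twelve weeks the correlation is only 0.3³ = 0.03 to 0.6³ = 0.22. For this route, however, the protocol asks for immediate EOS and entry.

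**The relapse may be real.** Protocol 4.1.2 mentions a non-treatment portion of the parent trial, so true loss of effect is plausible. Regression would then explain less of the later improvement. The mixing of regained and held response in Step 1 would remain.

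**The stakes are low.** The primary endpoint is treatment-emergent adverse events, no test is planned, and Protocol 3.2 already concedes that there is no placebo control and no control of observer bias. This limits the point to secondary efficacy reporting.

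A reader might infer that the Responders column as a whole is inflated by 40% to 60%, or that any improvement after re-entry is artefact. The documents support neither. Those percentages describe a subset that no planned table shows and that may be very small. Without a control group, regression to the mean cannot be separated from a true effect of re-treatment.

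**Conclusion.** The concern holds in limited form. On the preferred combined visit, taking immediate EOS to mean the visit at which the drop was scored, relapse entrants have the triggering score as their extension baseline. SAP 6.1 pools them with responders who completed Week 28. Their extension-baseline results therefore include regression to the mean and measure regaining rather than holding a response.

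The second part follows from the plan's own formula. The size of the first part rests wholly on assumed EASI variability, on how many patients relapse, and on what dropping to EASI 50 means numerically, since neither document gives a rule. Under the illustrative no-effect model the pooled column moves anywhere from negligibly to about 17 points in the median. The parent-baseline tables avoid the entry-day score, and the safety primary endpoint is not touched.

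**What to change.** 1. In SAP 6.1, group 2, split Responders into those who completed Week 28 and those who entered at loss of response. State how the entry route is derived from parent-trial data, and how the drop to EASI 50 was applied there.
2. Show the extension-baseline results for Responders and Overall Total with and without the second group.
3. For that group, lead with the already planned parent-baseline EASI75 at Week 48, and add Week-48 EASI against the patient's own parent Week-16 EASI.
4. Footnote the extension-baseline tables: for relapse entrants the baseline may be the score that triggered entry. For completers, selection can run the other way.

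The cost is SAP wording and one more table column. Parent baseline and Week-16 response are already needed for planned analyses, so no new visit or data collection should be required. The drawback is small cells: with about 40 patients the relapse group may hold only a few, and an individual listing may then be more useful than percentages.
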